### 14.3.9 Interim analysis

No interim analysis is planned.

### 14.3.10 General principles

All hypotheses will be tested at a one-sided 2.5% significance level. This will be done by calculating the two-sided 95% CIs and p-value (note that for the non-inferiority hypotheses a different approach will be used).

An observed-cases approach will be used for tabulations of data by visit (i.e., involving only those subjects who attended each specific visit).

Categorical data will be summarised using the number and percentage of subjects in each category and treatment group. Continuous data will be summarised using the mean, median, standard deviation, minimum and maximum values.

All the analyses specified in the protocol will be reviewed in relation to the blinded data actually obtained and the statistical analysis plan update will be finalised before breaking the randomisation code.

Any changes from the statistical analysis planned in this clinical trial protocol will be described and justified in a protocol amendment, the statistical analysis plan update and/or in the CTR dependent on the type of deviation.

### **14.3.11 Handling of missing values**

Procedures for handling of missing values are included under the sections describing the individual analyses.

## Appendix 1: Definitions of adverse events and serious adverse events

### Adverse event definition

*An AE is defined as any untoward medical occurrence in a patient or clinical investigation subject administered a pharmaceutical product and which does not necessarily have a causal relationship with this treatment. An AE can therefore be any unfavourable and unintended sign (including an abnormal laboratory finding), symptom, or disease temporally associated with the use of a medicinal (investigational) product, whether or not related to the medicinal (investigational) product. (ICH Harmonized Tripartite Guideline for Good Clinical Practice, E6 (R1)).*

This definition includes:

- Accidental injuries.
- Events related to trial procedures.
- Reasons for any unfavourable and unplanned change in medication (drug and/or dose).
- Clinically significant worsening of pre-existing conditions.
- Reasons for admission to hospital or surgical procedures unless these were planned before the subject consented to trial participation.
- AEs commonly observed and AEs anticipated based on the pharmacological effect of the IMP.
- Any laboratory abnormality assessed as clinically significant by the investigator (see Section [11.4.5](#)).

### Serious adverse event definition

An SAE is any untoward medical occurrence that

- Results in death.
- Is life-threatening.

- Requires inpatient hospitalisation or prolongation of existing hospitalisation. Planned hospitalisation or planned prolonged hospitalisation do not fulfil the criteria for being an SAE but should be documented in the subject's medical record.
- Results in persistent or significant disability/incapacity.
- Is a congenital anomaly/birth defect.

or

- Is a medically important condition. Events that may not be immediately life-threatening or result in death or hospitalisation but may jeopardise the subject or may require intervention to prevent one of the other outcomes listed in the definition above. Examples are intensive treatment in an emergency room or at home for allergic bronchospasm, blood dyscrasias and convulsions that do not result in hospitalisation, development of drug dependency or drug abuse.

Adverse events of special interest are described in Section [13.6.1](#).

## Appendix 2: Classification of adverse events

### Severity

The *severity* of the AE should be described in terms of mild, moderate or severe according to the investigator's clinical judgement.

Mild	An AE that is usually transient and may require only minimal treatment or therapeutic intervention. The event does not generally interfere with usual activities of daily living.
Moderate	An AE that is usually alleviated with additional specific therapeutic intervention. The event interferes with usual activities of daily living, causing discomfort but poses no significant or permanent risk of harm to the subject.
Severe	An AE that interrupts usual activities of daily living, or significantly affects clinical status, or may require intensive therapeutic intervention.

If the severity of an AE worsens, a new AE should be recorded.

### Causality

The *causal relation* of the AE to the use of the IMP (tralokinumab/placebo) should be described in terms of probable, possible, or not related according to the investigator's clinical judgement. The categories are defined below. Similarly, the causal relationship to each of the vaccines should be evaluated using the categories defined below (that is, probably related, possibly related, or not related).

Probably related	
Follows a reasonable temporal sequence from administration of the IMP.
 
Could not be reasonably explained by the subject's clinical state, environmental or toxic factors or other therapies administered to the subject.
 
Follows a known pattern of response to the IMP.
 
Disappears or decreases on cessation or reduction in dose of the IMP.
 
Reappears or worsens upon re-challenge.

------------------	---

Possibly related	Follows a reasonable temporal sequence from the administration of the IMP.  Could also be reasonably explained by the subject's clinical state, environmental or toxic factors or other therapies administered to the subject.  Follows a known pattern of response to the IMP.
Not related	Does not follow a reasonable temporal sequence from administration of the IMP.  Is better explained by other factors like the subject's clinical state, environmental or toxic factors or other therapies administered to the subject.  Does not reappear or worsen upon re-challenge.  Does not follow a known pattern of response to the IMP.

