### 13.4.2 LEO reporting responsibilities

Global Pharmacovigilance at LEO is responsible for assessing whether or not an SAE is expected. The relevant reference safety information documents for this clinical trial are:

- For the IMP (tralokinumab/placebo), the Investigator's Brochure, edition 17 and subsequent updates must be used.
- For the IMP (Tdap and meningococcal vaccines), the latest version of the approved labelling in the US must be used.

Global Pharmacovigilance at LEO will notify the regulatory authorities and concerned investigators of SAEs according to the current applicable legislation for the concerned countries.

The IRB(s) will be notified of SAEs according to the current applicable legislation for the concerned countries.

For all countries except the US, the following reporting requirements apply: all SAEs which are assessed as causally related to the IMP(s) **by either the investigator or LEO** (ICH E2A Guideline), and which are unexpected (Suspected, Unexpected Serious Adverse Reactions [SUSARs]), are subject to expedited reporting to regulatory authorities and IRB(s) according to the current applicable legislation in the concerned countries. Investigators will be notified of the evolving safety profile of the IMP on an ongoing basis.

For the US, the following reporting requirements apply: all SAEs which are assessed as causally related to the IMPs **by LEO** (Guidance for Industry and Investigators - Safety Reporting Requirements for INDs and BA/BE Studies; Guidance for Clinical Investigators, Sponsors, and IRBs: Adverse Event Reporting to IRBs – Improving Human Subject Protection) and which are unexpected (Serious and Unexpected Suspected Adverse Reactions [IND safety report]) are subject to expedited reporting to regulatory authorities and IRB(s). Investigators will be notified of the evolving safety profile of the IMP on an ongoing basis.

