### 13.7 Follow-up for final outcome of adverse events

During the trial, the investigator should follow up for final outcome on all AEs (including SAEs). Once a subject leaves the clinical trial, the investigator should follow up on the outcome of all non-serious AEs classified as of possible/probable relationship to the IMP for 2 weeks or until the final outcome is determined, whichever comes first. SAEs must be followed up until a final outcome has been established, that is, the follow-up may continue beyond the end of the clinical trial. For SAEs which have stabilised and cannot be expected to recover during study or safety follow-up periods, for example chronic illnesses, the final outcome should be reported as ‘not recovered’. In addition, a statement that the SAE has stabilised or is chronic should be added to the narrative description of the SAE on the SAE form.

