#### **14.3.8.1 Adverse events**

AEs will be coded during the course of the trial according to Medical Dictionary for Regulatory Activities (MedDRA). AEs will be presented by preferred terms and primary system organ class (SOC).

Treatment-emergent AEs will be summarised, however, all AEs recorded during the course of the trial will be included in the subject data listings. An event will be considered treatment-emergent if started after the first use of IMP or if started before the first use of IMP (applicable if subject had a wash-out) and worsened in severity thereafter. The tabulations described in the following will only include the treatment-emergent events. In each of the tabulations, AEs will be defined by MedDRA preferred terms within primary SOC.

An overall summary of the number of treatment-emergent AEs, number (percentage) of subjects with any treatment-emergent AEs, SAEs, deaths, premature discontinuations from the trial due to AEs, treatment-related AEs and severe AEs will be presented.

The number of AEs and the number of subjects experiencing each type of AE will be tabulated by treatment group. The percentage of subjects with AEs will be compared between treatment groups by a chi-square test or Fisher's exact test (if expected cell count < 5).

The severity for each type of AE will be tabulated by treatment group.

The causal relationship to IMP (tralokinumab/placebo) for each type of AE will be tabulated by treatment group. Related AEs are defined as AEs for which the investigator has not described the causal relationship to IMP as 'not related'. The number of related AEs and the number of subjects experiencing each type of related AE will be tabulated. The percentage of subjects with related AEs will be compared between treatment groups by a chi-square test or Fisher's exact test (if expected cell count <5).

The causal relationship to IMP (each vaccine) for each type of AE will be tabulated by treatment group. Related AEs are defined as AEs for which the investigator has not described the causal relationship to IMP as 'not related'. The number of related AEs and the number of subjects experiencing each type of related AE will be tabulated. The percentage of subjects with related AEs will be compared between treatment groups by a chi-square test or Fisher's exact test (if expected cell count <5).

SAEs and AESIs will be evaluated separately and a narrative for each will be given. AEs leading to withdrawal from trial will be listed.

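### Appendix 2 lists a known pattern of response under both related categories, so a new type of reaction has no defined route to 'related' and is steered towards 'not related'

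*Protocol*

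**What the plan says.** Appendix 2 of the protocol asks for the causal relation of each AE to tralokinumab/placebo to be given as "probable, possible, or not related according to the investigator's clinical judgement", and applies the same three categories to each vaccine. Three of its statements matter here:

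- Under 'probably related' and again under 'possibly related': "Follows a known pattern of response to the IMP".
- Under 'not related': "Does not follow a known pattern of response to the IMP".
- Also under 'not related': "Does not follow a reasonable temporal sequence from administration of the IMP".

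Section 13.3 requires AEs to be classified by the Appendix 2 definitions.

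The classification is used in three places:

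- **Section 14.3.8.1 (analysis):** "Related AEs are defined as AEs for which the investigator has not described the causal relationship to IMP as 'not related". Related AEs are tabulated and tested between arms, once for tralokinumab/placebo and once for the vaccines. SAP section 6.8.1 adds no other definition of causality.
- **Section 13.7 (follow-up):** once a subject has left the trial, the investigator follows "all non-serious AEs classified as of possible/probable relationship to the IMP for 2 weeks", or until the outcome is known if that is sooner.
- **Section 13.4.2 (expedited reporting):** outside the US, serious AEs (SAEs) judged causally related by the investigator or by the sponsor, and "which are unexpected (Suspected, Unexpected Serious Adverse Reactions [SUSARs]), are subject to expedited reporting".

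**The concern.** A reaction that is new to a product has, by definition, no known pattern with that product. If a known pattern is one of the marks of even a possible relation, and its absence is a mark of no relation, the definitions point the wrong way for the events that safety monitoring most needs to find.

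This bears on the present trial. One stated objective is to evaluate the safety of tralokinumab given together with two vaccines (Panel 3), and an effect of the combination may have no known pattern yet. Section 5.6 describes several risks, such as immune complex disease and severe infections, as theoretical. The protocol does not say whether a theoretical risk counts as a known pattern, so investigators at about 40 sites may decide differently.

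At stake are the prespecified related-AE summaries, a limited part of AE follow-up, and one of the two causality triggers for expedited reporting outside the US. The trial runs in the US and Canada (section 7.2), so that trigger is in use.

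**Working it through.** The plan gives no figure to reproduce, and the point depends on no rate, margin or sample size. The check is a reading of the definitions against a test case: an AE with plausible timing, no other explanation, and no known pattern of response.

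**1. Test case against each category**

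| Statement | Probably related | Possibly related | Not related | Test case |
|---|---|---|---|---|
| Timing | reasonable | reasonable | not reasonable | reasonable |
| Other explanation | none reasonable | could also explain it | better explains it | none |
| Known pattern | yes | yes | no | no |

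The case misses the known-pattern statement in both related categories. It matches one 'not related' statement (no known pattern) and fails two (timing and better explanation).

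**2. What follows on each reading**

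- *Every statement must hold:* the case fits no category.
- *One 'not related' statement is enough for that class:* the case is 'not related'.
- *The statements guide clinical judgement:* the investigator may choose 'possibly related', but the pattern statement counts against it.

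On none of the three do the definitions themselves lead the case to a related category.

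**3. How far the strict reading can be pressed**

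Cross timing (2 levels), other explanation (3) and known pattern (2): 2 × 3 × 2 = 12 profiles. If all three statements must hold, 1 profile is probable, 1 possible and 1 not related, so 12 − 3 = 9 fit nothing. Of the 6 profiles with a known pattern, 2 reach a related category and 4 fit nothing. Of the 6 without one, none reaches a related category, 1 is 'not related' and 5 fit nothing. This count leaves out the de-challenge and re-challenge statements.

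The count shows two things. No profile without a known pattern meets either related definition. The strict reading is also unworkable in general, because it leaves even known-pattern events unclassified. The vaccines confirm this: 'probably related' includes "Reappears or worsens upon re-challenge", yet each vaccine is given once (section 7.1), so on a strict reading no AE could ever be probably related to a vaccine.

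**4. Where the classification does and does not reach**

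| Output | Depends on investigator causality? |
|---|---|
| Related-AE tables and tests (14.3.8.1) | Yes |
| Follow-up of non-serious AEs after leaving the trial (13.7) | Yes |
| Expedited reporting outside the US (13.4.2) | One of two triggers |
| Expedited reporting in the US (13.4.2) | No, sponsor's assessment |
| Sending SAEs to the sponsor within 24 hours (13.4.1) | No, all SAEs |
| Table and test of all treatment-emergent AEs (14.3.8.1) | No |
| AE follow-up during the trial (13.7) | No |

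**The case against.** A reader might infer that a new reaction cannot be classed as related at all, and that unexpected-reaction reporting would miss it. The documents do not support either statement.

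- **Judgement.** Assignment is by clinical judgement, and no text says that every statement must be met. An all-criteria rule could not work for single-dose vaccines. This stands, and it rules out 'cannot'. It does not remove the pull of the wording, because section 13.3 ties the judgement to these definitions and nothing marks a known pattern as optional.
- **Default to related.** Section 14.3.8.1 counts an AE as related unless the investigator chose 'not related', so an event that fitted no category and was left unclassified would be counted. This also stands, but Appendix 2 offers three answers and asks for one of them. The loss arises when the investigator picks 'not related', which is where the wording leans.
- **Serious events.** Every SAE reaches the sponsor whatever its causality. The sponsor judges expectedness, and its causality assessment is sufficient outside the US and decisive in the US. This stands. What is left is a weaker investigator trigger. The documents do not say which causality criteria the sponsor applies.
- **Main safety comparison.** The safety endpoint is the number of AEs, and all treatment-emergent AEs are compared by arm. Both arms receive both vaccines, so an effect of the combination would be counted there. This stands and confines the problem to the related-AE summaries.
- **Follow-up.** The loss is at most 2 weeks for non-serious AEs. For a subject who stays to Week 30 it begins 30 − 12 = 18 weeks after vaccination. For one who transfers to the extension trial at Week 16 it begins 16 − 12 = 4 weeks after. The effect is small in either case.

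**Conclusion.** The point holds as a defect in a stated definition. Under Appendix 2 a new type of reaction with plausible timing has no defined route to 'probably' or 'possibly' related, and one statement points it to 'not related'. The likely effect is downward: fewer events in the related-AE tables and tests for tralokinumab/placebo and for each vaccine, some non-serious events not followed after the subject leaves, and a weaker investigator trigger for expedited reporting outside the US.

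The size cannot be given. The documents offer no basis for estimating how many AEs would be new in type, or how often investigators would follow the wording over their own judgement. No primary endpoint, analysis set or hypothesis in the testing hierarchy is affected.

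The conclusion assumes that investigators use Appendix 2 as section 13.3 directs, and that no training or site material tells them a known pattern is optional. The change should be made because it is cheap and the affected outputs are prespecified safety analyses.

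**What to change.** In Appendix 2, Causality:

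1. Remove the known-pattern statement from 'possibly related', or keep it and add that a known pattern supports this class but is not required for it.
2. State that the absence of a known pattern is not by itself a ground for 'not related'.
3. State that both points apply to tralokinumab/placebo and to each vaccine.

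There is no need for a rule that plausible timing alone makes an AE at least possibly related. The investigator's judgement can stay as it is.

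The cost is a protocol wording change and a reminder to sites. Somewhat more AEs will be classed as possibly related, in both arms, since investigators are blinded. No analysis method changes.

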## Outcome

The *outcome* of the event according to the investigator's clinical judgement should be classified using the categories below.

Recovered/ resolved	The event has stopped. The stop date of the event must be recorded.
Recovering/ resolving	The subject is clearly recovering from an event. The event is not yet completely resolved.
Not recovered/ not resolved	Event is still ongoing.
Recovered/ resolved with sequelae	The event has reached a state where no further changes are expected and the residual symptoms are assumed to persist. An example is hemiparesis after stroke.  The stop date of the event must be recorded. In case of a SAE, the sequelae should be specified.
Fatal	The subject has died as a consequence of the event. Date of death is recorded as stop date for the AE.
Unknown	Unknown to investigator, e.g. subject lost to follow-up.

Note that as per the above definition, LEO uses “recovered/resolved” only if an event has actually stopped. According to the CDISC definition, the category “recovered/resolved” also includes events which have improved. However, following the LEO definitions above, such an improved event will instead be classified as “not recovered/not resolved” or “recovering/resolving”.

Similarly, it should be noted that as per the above definition, LEO uses “recovered/resolved with sequelae” only if an event has reached a state where the residual symptoms are assumed to persist. According to CDISC, an event is considered “with sequelae”, if it has “retained pathological conditions”. Consequently, it is likely that some of the events classified by LEO with the outcome “recovered/resolved with sequelae” could have been classified with the outcome “recovered/resolved” according to the CDISC definition.

For SAEs which have stabilised and cannot be expected to recover during study or safety follow-up periods, for example chronic illnesses, the final outcome should be reported as ‘not recovered’. In addition, a statement that the SAE has stabilised or is chronic should be added to the narrative description of the SAE on the SAE form.

## Appendix 3: Trial governance considerations

### Appendix 3A: Regulatory and ethical considerations

This trial will be conducted in accordance with the protocol and with the following:

- Consensus ethical principles derived from international guidelines including the current version of the Declaration of Helsinki (38) and Council for International Organizations of Medical Sciences (CIOMS) International Ethical Guidelines (39).
- Current version of applicable International Council for Harmonisation (ICH) Good Clinical Practice (GCP) Guidelines (40).
- EU's General Data Protection Regulation 2016/679 of 27 April 2016.
- Applicable laws and regulations.

The appropriate regulatory authorities must be notified of/approve the clinical trial as required.

Any documents that the IRB may need to fulfil its responsibilities (such as the trial protocol, protocol amendments, Investigator's Brochure, subject information leaflet, ICFs, or advertisements) will be submitted to the IRB. These documents must be reviewed and approved by the IRB before the trial is initiated.

Any amendments to the protocol must be approved by/receive favourable opinion from relevant regulatory authorities and IRBs, as required, prior to implementation.

The principal investigator will be responsible for the following, if required by local legislation:

- Providing written summaries of the status of the trial to the IRB annually or more frequently in accordance with the requirements, policies, and procedures established by the IRB.
- Notifying the local IRB of SAEs or other significant safety findings as required by IRB procedures.
- Providing oversight of the conduct of the trial at the trial site and adhering to applicable national and international legislation.

